4.3 Blinding

This is an open-label study; no blinding will be employed.

4.4 Method of Assignment of Subjects to Treatment Arms

This study consists of a single prospective treatment arm, to which all eligible subjects are assigned. A historical control arm, consisting of patients treated with antibiotics for recurrent CDI, will also be used for efficacy analysis. [REDACTED]

[REDACTED] No randomization is employed in this study.

4.5 Determination of Sample Size

Approximately up to 150 subjects will be enrolled in this study and receive RBX2660; and another 100 historical controls with recurrent CDI diarrhea will also be included in the study based on a retrospective chart review.

The primary analysis will compare the proportion of subjects in the treatment arm who are recurrence-free to the proportion of historical controls who are recurrence-free. [REDACTED]

[REDACTED]
[REDACTED]
[REDACTED]
[REDACTED]

[REDACTED]

[REDACTED]

[REDACTED]

4.7 Treatment Arms

The open-label study consists of a single prospective treatment arm and historical control group, as described below.

- One treatment with RBX2660: one treatment consists of two enemas of RBX2660 administered 7 ± 2 days apart (the second enema may be administered sooner if CDI diarrhea reoccurs in less than 7 days). [REDACTED]
- Historical control group chosen from a retrospective chart review.

5 CHANGES IN THE CONDUCT OF THE STUDY OR PLANNED ANALYSES

5.1 Changes in the Conduct of the Study

The SAP was previously updated to allow an historical control arm of approximately 100 subjects to be included in the study. These subjects were chosen from retrospective chart reviews to obtain a closely matched data set of the standard of care antibiotic treatment for recurrent CDI to the RBX2660 treated subjects based on a number of baseline factors. The historical control arm allows for efficacy comparisons to be performed.

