### 6.10 Antibiotic-treated Historical Control

The efficacy of RBX2660 will be evaluated by comparing the recurrence-free rate observed in the study population to the recurrence-free rate identified from antibiotic-treated historical controls. A chart review will be conducted by Rebiotix or its designees to gather the historical control data to be used in the comparison. The historical control protocol can be found in Appendix 1 to this study protocol.

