**A1. Description of the Historical Control Study**

“An Open-label Efficacy and Safety Assessment of Rebiotix RBX2660 (microbiota suspension) for the Treatment of Recurrent *Clostridium difficile* Infection Protocol #2015-01” is a prospective, multicenter, open-label study assessing RBX2660 as an adjunct to antibiotics for the treatment of recurrent CDI. Efficacy of RBX2660, measured by the recurrence-free rate of CDI diarrhea without the need for retreatment with *C. difficile* anti-infective therapy or fecal transplant through 56 days after completion of study treatment with RBX2660, will be evaluated by comparing the recurrence-free rate observed in the study population to the recurrence-free rate identified from antibiotic-treated historical controls. A chart review will be conducted by qualified and trained site personnel to gather the historical control data to be used for the comparison. Safety data on the antibiotic-treated historical controls will also be gathered, but as it is expected that such data may be scant, they will not be used for comparison purposes but will be reported for informational purposes.

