#### **A4. Study Design and Methods**

This is a retrospective chart review of patients treated with antibiotics for recurrent CDI who match key inclusion/exclusion criteria from the clinical study (see below). Patients will not be contacted. A waiver of Informed Consent/HIPAA authorization for the collection of chart data will be obtained from each site's IRB prior to beginning the chart review process. Site personnel will review their patient databases and identify patients with a diagnosis of multi-recurrent CDI, which is defined as a documented diagnosis of the return of CDI diarrhea ( $\geq 3$  watery stools in  $\leq 24$  hours for at least two consecutive days) that begins less than 8 weeks after completion of a CDI treatment regimen that resulted in the cessation of CDI symptoms. The diagnosis must include at least one positive *C. difficile* test on record. The identified charts will be accessed by the designated qualified and trained chart reviewer at the site. All patient records

on the list will be reviewed and a log will be kept documenting the review and why a record was excluded from the final historical control data set.

Data collection includes:

- demographics (age at the time of the start of data collection, gender, race, ethnicity);
- pre-existing conditions;
- concomitant medications;
- CDI history including each episode's start/stop dates, signs/symptoms, treatment(s) received, outcomes, and CDI-related hospitalizations;
- Blood and stool test results;
- Vital signs;
- Adverse events as recorded in the chart. (see Section 7.0 of the study protocol for all definitions). Adverse events will be adjudicated for seriousness, severity, and causality by the site investigator at the time of data collection as best as possible given the description of the event in the medical record.

[REDACTED]

All data and records will be kept in strict confidentiality as required by law and as stated in Section 9.4 of the study protocol.

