**A7. Statistical Considerations**

Approximately up to 200 subjects (minimum of 100) will be included in the historical control group to appropriately power the primary efficacy study endpoint (see Section 8.0 Statistical Considerations in the study protocol and the Statistical Analysis Plan).

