4 STUDY DESIGN

4.1 General Design

This is a prospective, multicenter, open-label study assessing the efficacy and safety of RBX2660 as an adjunct to antibiotics for the treatment of recurrent CDI. Up to approximately 150 subjects will be enrolled in this study and receive RBX2260. Approximately 100 historical controls will be chosen from a retrospective chart review of patients treated with antibiotics for recurrent CDI who match key inclusion/exclusion criteria from the study.

Subjects who meet all inclusion and exclusion criteria, including having a positive *C. difficile* test within 60 days prior to enrollment and experiencing either a) at least two recurrences after a primary episode (diagnosis must include at least one positive *C. difficile* test on record within 60 days prior to enrollment) and have completed at least two rounds of standard-of-care oral antibiotic therapy or b) have had at least two episodes of severe CDI resulting in hospitalization prior to enrollment, will receive open-label treatment with RBX2660. One study treatment consists of two RBX2660 enemas administered 7 ± 2 days apart; the second enema may be administered sooner if CDI diarrhea reoccurs in less than 7 days. Subjects will already be taking or will start a course of antibiotics to control recurrent CDI diarrhea at the time of enrollment, [REDACTED]

[REDACTED] An in-office follow-up visit will occur at 8 weeks after completing study treatment for the assessment of AEs, efficacy, collection of the Subject Diary, and blood tests. Telephone assessments for AEs including serious adverse events (SAEs) and the new onset of chronic diseases and CDI symptoms will occur at weeks 1, 2, 3, and 4 and at 3, 6, and 12 months after completing study treatment. Assessment of serious adverse events and the new onset of chronic diseases will occur via phone call at 24 months after completing study treatment. Subjects will keep a detailed Subject Diary to assess for solicited adverse events from the date of enrollment to one week after completing study treatment (second enema). Treatment

failures (as determined by the site investigator at the time of CDI recurrence) are eligible to receive another therapy deemed most appropriate by their study investigator.

[REDACTED]

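### No visible rule stops the historical controls from being selected, or their number settled, with outcomes already in view

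*SAP*

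**What the plan says.** **How controls enter.** Protocol A4 has site staff list patients with multi-recurrent CDI and review every record: those "on the list will be reviewed and a log will be kept documenting the review", with the reason for each exclusion. A6.1 and A6.2 give the eligibility criteria. SAP 4.1 says "Approximately 100 historical controls will be chosen from a retrospective chart review of patients treated with antibiotics for recurrent CDI", subject to the key criteria. SAP 5.1 goes further: "These subjects were chosen from retrospective chart reviews to obtain a closely matched data set", matched to the treated subjects on baseline characteristics it does not name.

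**How many.** Protocol A7: "Approximately up to 200 subjects (minimum of 100) will be included in the historical control group". SAP 4.5: "another 100 historical controls with recurrent CDI diarrhea will also be included in the study". SAP 4.1 and 5.1 also say about 100.

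**Who reviews.** Protocol 6.10: "A chart review will be conducted by Rebiotix or its designees". Protocol A1: "A chart review will be conducted by qualified and trained site personnel". A4 agrees with A1.

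**What the abstractor sees.** The A4 data list includes, for each CDI episode, the treatment given and its outcome.

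**The concern.** The trial is open-label and non-randomised, so the validity of the primary comparison depends on how controls enter. The control success rate is the benchmark, and the charts already contain it.

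If more records qualify than are needed, someone decides which ones count as a close match and when to stop. No visible text requires these decisions to be made without knowledge of the outcome, or before treated-arm results are known. Those results accrue unblinded, and Protocol 8.3 plans an efficacy look when about 100 treated subjects reach 8 weeks.

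One criterion adds to this. The A6.2 exclusion for diarrhea that continued despite CDI antibiotics has no time anchor for controls, unlike the exclusions for prior successful transplant, abdominal surgery and life expectancy. It could therefore be judged with the result of the comparison course in view.

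If recurrence-free charts are even slightly less likely to be kept, the benchmark drops and RBX2660 looks better than it is. No intent is needed, because judgments about match quality or chart completeness can track outcome.

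**Working it through.** **The plan's own figure.** A7 says the control number is chosen to power the primary endpoint. That cannot be reproduced, because alpha, power and assumed rates are not visible in Protocol 8.1/8.3 or SAP 4.5. What follows is illustration under stated assumptions.

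**Inputs**
- True success p = 35% in both groups, so there is no treatment effect. This is an assumption, taken as 1 − 65% from the recurrence rate after two relapses in Protocol A3.
- Treated n = 150 (Protocol 3.2; SAP 4.1). Control n_C = 100 (SAP) or 200 (upper figure in A7).
- Two-sided test at 0.05 (assumed), so 2.5% in favour of RBX2660.
- r = probability of inclusion for a recurrence-free chart divided by that for a recurrence chart (assumed 1, 0.9, 0.8).

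**Step 1: control rate after selection.** p_C = p·r / (p·r + 1 − p).
- r = 0.9: 0.315/0.965 = 32.6%
- r = 0.8: 0.280/0.930 = 30.1%

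**Step 2: false positives favouring RBX2660.** P = 1 − Φ[(1.96·s0 − d)/s1], where
- d = 0.35 − p_C
- s0 = √[p̄(1−p̄)(1/n_C + 1/150)], with p̄ the pooled rate
- s1 = √[p_C(1−p_C)/n_C + 0.35·0.65/150]

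For r = 0.8 and n_C = 100: d = 0.0489, p̄ = (30.1 + 52.5)/250 = 0.330, s0 = 0.0607, s1 = 0.0602. Then (0.1190 − 0.0489)/0.0602 = 1.165, and P = 12.2%.

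| r | Control rate | P, 100 controls | P, 200 controls |
|---|---|---|---|
| 1 | 35.0% | 2.5% | 2.5% |
| 0.9 | 32.6% | 5.7% | 6.7% |
| 0.8 | 30.1% | 12.2% | 16.2% |

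More controls make it worse: the shift stays the same while the standard error shrinks. With a true rate of 50% and r = 0.8, the control rate is 44.4% and P is 13.5% (100) or 17.6% (200).

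**Step 3: open size alone, charts in random order (40,000 simulated trials).**
- Stopping at the lowest running rate between 100 and 200 lowers the average control rate from 40% to 37.4% (from 35% to 32.5%).
- With p = 35%, taking whichever of 100 or 200 favours RBX2660 gives 3.9% false positives. Stopping at any favourable number from 100 to 200 gives 6.3%.

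Full use of this freedom, with hindsight at every chart, does about as much as r = 0.9 and well under r = 0.8.

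**The case against.** **Redaction.** A4 has a blacked-out block after the data list, SAP 4.4 is cut after it introduces the control arm, and SAP 4.5 is cut after the primary comparison. A selection or sizing rule could sit in any of them. This stands: the point is that no rule is visible, not that none exists.

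**A benign reading of the visible text.** SAP 4.1 ties its wording to the key eligibility criteria. Combined with A4's full review, its exclusion log and the A6 checklists, it could mean that every eligible record enters. That is a fair reading of SAP 4.1. It does not cover SAP 5.1, which adds matching on unnamed factors. The log makes decisions auditable but does not keep them blind to outcome.

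**Stronger readings a reader might infer, which the documents do not support**
- *That the control numbers contradict each other.* About 100 lies inside A7's range of 100 to about 200.
- *That the sponsor picked the controls.* Protocol 6.10 refers the reader to Appendix 1, which assigns the work to site staff, and site staff may be designees. The passages need reconciling; they are not evidence of sponsor selection.
- *That controls were picked by outcome.* Nothing shows this.
- *That no analysis could undo such a bias.* An analysis of the chosen set alone could not, but a complete A4 log would allow all eligible records to be analysed.

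**Conclusion.** The concern holds as an open route to bias. On the visible text, inclusion, matching and final number can all be settled by people who can see whether the patient recurred.

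The main lever is outcome-related inclusion. Under the assumptions above, r of 0.9 or 0.8 adds 2.4 or 4.9 points to the apparent benefit (35.0 − 32.6; 35.0 − 30.1). It raises false positives from 2.5% to 5.7% or 12.2% with 100 controls, and to 6.7% or 16.2% with 200. Open size is the lesser and bounded lever.

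The values of r are illustrative; the documents give no basis for estimating them. If the true difference is large, a shift of this size would inflate the estimate without changing the conclusion of the test. The finding depends on the redacted passages not already containing an outcome-blind rule.

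**What to change.** 1. In Protocol A4 and A7 and SAP 4.1, 4.5 and 5.1, state one rule: every logged record meeting A6.1/A6.2 enters the control set, or a fixed number enters in a stated order that does not depend on outcome.
2. Define the index antibiotic course for controls. Decide eligibility, and any matching on named factors, only from data up to that course.
3. Lock the list before the 56-day outcome is abstracted.
4. Make Protocol 6.10 agree with A1/A4 that site reviewers decide inclusion.
5. If selection is already complete, as the past tense in SAP 5.1 suggests, run the primary comparison on all eligible logged records. Show the matched subset as a sensitivity analysis and report exclusions by outcome.

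If the redacted text already holds such a rule, a cross-reference is enough for items 1 to 3.

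The cost is wording, a two-step abstraction form and possibly slightly looser matching. Item 5 requires the log to be complete and outcomes to be abstracted for eligible records that were left out.

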6 BASELINE, EFFICACY AND SAFETY EVALUATIONS

6.1 Schedule of Events

Activity	Visit 1 Screening	Visit 2 Baseline/ First Enema	Visit 3 Second Enema 7 ± 2 days after Visit 2	Visit 4 8-Week (± 7 days)	Phone Assessment (Weeks 1, 2, 3, and 4 (± 3 days)) ²	Phone Assessment at 3, 6, 12, and 24 months (± 7 days) after Visit 3 ³
Informed consent obtained	X					
Demographics, medical history	X					
Prescribe/continue antibiotics for CDI symptom control	X					
[REDACTED]	[REDACTED]	[REDACTED]	[REDACTED]	[REDACTED]	[REDACTED]	[REDACTED]
[REDACTED]	[REDACTED]	[REDACTED]	[REDACTED]	[REDACTED]	[REDACTED]	[REDACTED]
Pregnancy testing performed	X	X	X			
Form SF-36 administered	[REDACTED]			[REDACTED]		
Inclusion/exclusion criteria confirmed	X	X				
[REDACTED]		[REDACTED]				
RBX2660 administered		X	X			
Recurrence of CDI symptoms assessed		X	X	X	X	X
Vital signs assessed	X	X	X	X		
Subject Diary reviewed and collected ¹	X ¹	X ¹	X ¹	X ^{1,5}		
Concomitant medications	X	X	X	X	X	X
AEs/SAEs assessed	X	X	X	X	X	X
Review of Pre-existing Conditions				X		X

¹ Solicited AEs are collected through 7 days after last treatment with RBX2660. Review the Diary at each visit and collect completed pages at Visits 2, 3, and 4.

[REDACTED]

[REDACTED]

[REDACTED]

[REDACTED]
[REDACTED]
[REDACTED]
[REDACTED]

[REDACTED]
[REDACTED]

[REDACTED]
[REDACTED]

[REDACTED]

[REDACTED]
[REDACTED]
[REDACTED]
[REDACTED]
[REDACTED]

[REDACTED]	[REDACTED]	[REDACTED]	[REDACTED]
[REDACTED]	[REDACTED]	[REDACTED]	[REDACTED]
[REDACTED]	[REDACTED]	[REDACTED]	[REDACTED]
[REDACTED]	[REDACTED]	[REDACTED]	[REDACTED]
[REDACTED]	[REDACTED]	[REDACTED]	[REDACTED]
[REDACTED]	[REDACTED]	[REDACTED]	[REDACTED]
[REDACTED]	[REDACTED]	[REDACTED]	[REDACTED]
[REDACTED]	[REDACTED]	[REDACTED]	[REDACTED]

[REDACTED]	[REDACTED]	[REDACTED]	[REDACTED]
[REDACTED]	[REDACTED]	[REDACTED]	[REDACTED]
[REDACTED]	[REDACTED]	[REDACTED]	[REDACTED]

[REDACTED]

[REDACTED]

[REDACTED]

[REDACTED]

[REDACTED]

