**6.8 8-Week Office Visit (Visit 4)**

Subjects return to the study site for the 8-week follow-up visit after completing study treatment with RBX2660. [REDACTED]

[REDACTED] At this visit, reoccurrence of CDI and adverse event information is assessed, a review of medication changes and pre-existing conditions is conducted, and the SF-36 Form is administered. The assessment of pre-existing conditions includes discussion with the subject to determine if the condition is improved, unchanged, worsened or resolved since completion of study treatment. The Subject Diary is collected and reviewed with the subject. [REDACTED] If CDI reoccurrence is suspected < 56 days after completing study treatment, the investigator assesses for recurrence using the four criteria in Section 3.6. The need for retreatment for *C. difficile* infection in the absence of a positive stool test for *C. difficile* will be made by the study investigator so that the appropriate treatment of the subject can be quickly administered in the case of failure to avoid serious adverse events, including hospitalization or death. If the subject does not have reoccurrence of CDI before 56 days after completing study treatment, s/he is considered a treatment success (see Section 3.5). [REDACTED]

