## 7.2 Assessment of Efficacy

The primary efficacy parameter is treatment success, defined as the absence of CDI diarrhea without the need for retreatment with *C. difficile* anti-infective

therapy or FT through 56 days after the completion of study treatment (Visit 3). Some subjects may continue to have short bouts of diarrhea before the 56-day time point, but most if not all will be resolved within 30 days after receiving RBX2660. The efficacy assessment will occur at the 8-week office visit.

[REDACTED]  
[REDACTED]  
[REDACTED]

[REDACTED] See Sections 6.10 and 8.0 of this protocol and the separate Statistical Analysis Plan for additional details on the efficacy assessment.

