4.1.3 Definition of Treatment Success

Treatment success is defined as the absence of CDI diarrhea without the need for retreatment with *C. difficile* anti-infective therapy or FT through 56 days after completion of study treatment.

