4.1.4 Definition of Treatment Failure (CDI Recurrence)

Treatment failure (CDI recurrence) is defined as: 1) the presence of CDI diarrhea (see Section 4.1.2), with or without other CDI symptoms, < 56 days after administration of the last assigned study enema; 2) a positive stool test for *C. difficile*; 3) need for retreatment for *C. difficile* infection; and 4) no other cause for CDI symptoms has been determined. [REDACTED]

[REDACTED]

[REDACTED]
[REDACTED]

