6.3 Analysis Populations

Enrolled Population: includes all subjects enrolled into the study, including subjects in the historical control arm.

Safety Population: includes all subjects enrolled into the study who received any study treatment with RBX2660; this does not include subjects in the historical control arm.

Full Analysis Set (FAS) Population: includes the Safety Population and subjects in the historical control arm.

Evaluable Population: includes the FAS subjects who were evaluable for treatment outcome (e.g., exclude subjects that discontinued from the study prior to determination of treatment failure and were not followed for at least 56 days (day 49 – 63) after the last treatment date).

Per Protocol Population: includes subjects from the Evaluable Population, excluding:

- Subjects from the Safety Population that did not complete 2 enemas

- Subjects that received fecal microbiota transplant before the 8-week follow-up and lacked a documented recurrence of CDI (Treatment Failure eCRF)
- Violations to the inclusion or exclusion criteria, including protocol definition of recurrent CDI two hospitalizations for CDI or 3 recurrent CDI events
- Received prohibited medication during the 8-week follow-up period

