8.7 Analysis of Efficacy

8.7.1 Treatment Success

Treatment success is the primary efficacy endpoint and the analyses will be performed on the Evaluable Population. The primary endpoint will be summarized by frequencies and percentages

[REDACTED]

[REDACTED] The analysis of efficacy will be repeated using the Full Analysis Set and Per Protocol populations. Sensitivity analyses will also be conducted using the Full Analysis Set where missing responses are imputed using a best-case scenario where missing responses are treated as successes.

[REDACTED]

[REDACTED]

[REDACTED]

[REDACTED]

[REDACTED]

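### SAP 6.3 accepts follow-up to day 49 as 56 days, so a subject seen on days 49–55 can count as a primary-endpoint success with up to 7 days of the window unobserved

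*SAP*

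**What the plan says.** SAP 4.1.3 defines success as no CDI diarrhea and no need for "anti-infective therapy or FT through 56 days after completion of study treatment". SAP 4.1.4 defines failure by diarrhea occurring "< 56 days after administration of the last assigned study enema", which ends one day earlier.

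Protocol 7.2 fixes when the outcome is judged: "The efficacy assessment will occur at the 8-week office visit". The schedule in SAP 6.1 gives that visit as "Visit 4 8-Week (± 7 days". Protocol 6.8 states the scoring rule: "If the subject does not have reoccurrence of CDI before 56 days after completing study treatment, s/he is considered a treatment success".

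SAP 8.7.1 names the analysis set: "Treatment success is the primary efficacy endpoint and the analyses will be performed on the Evaluable Population". SAP 6.3 excludes from that set subjects who discontinued before a failure was determined and "were not followed for at least 56 days (day 49 – 63) after the last treatment date".

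The scheduled calls before Visit 4 end at week 4 (± 3 days). The next scheduled contact after Visit 4 is the 3-month call (± 7 days), at which SAP 6.1 marks recurrence of CDI symptoms as assessed.

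**The concern.** Days 49 to 55 are not at least 56 days, so the SAP 6.3 definition contradicts itself, and it does so in the primary analysis set. A subject judged on one of those days is judged before the endpoint window has closed. If that subject then leaves the study, the remaining days are never observed, yet the subject is not excluded and can be scored a success.

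Within the RBX2660 arm the error has one direction: an unobserved day can hide a failure but cannot create one. The study is open-label, has no randomized control and relies on the investigator to determine the outcome, so a removable error toward success is worth removing. The one sensitivity analysis visible in SAP 8.7.1 cannot detect it. It imputes missing responses as successes, and these subjects are not counted as missing in the first place.

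**Working it through.** **The plan's own range.** 8 weeks × 7 = day 56; 56 − 7 = 49 and 56 + 7 = 63. The range in SAP 6.3 is therefore the Visit 4 window carried over into the definition of adequate follow-up.

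**Days unobserved after a visit on day 49.**
- Success wording (through day 56): 56 − 49 = 7 days, or 7/56 = 12.5% of the window.
- Failure wording (last countable day 55): 55 − 49 = 6 days.

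CDI diarrhea also needs two consecutive days (SAP 4.1.2), so an episode that starts on day 49 cannot be confirmed at a day-49 visit.

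**Assumptions for size.** The visible documents give no recurrence rate for RBX2660 and no distribution of visit days. I assume 20–30% recurrence by day 56, onsets spread evenly over 56 days, up to 150 treated subjects (SAP 4.5), and no detection after Visit 4.

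**Visits uniform over the 15 days from 49 to 63.** The mean number of unobserved days is the sum of the gaps divided by 15.
- Success wording: (7+6+5+4+3+2+1)/15 = 28/15 = 1.87 days; 1.87/56 = 3.3% of recurrences.
- Failure wording: (6+5+4+3+2+1)/15 = 21/15 = 1.4 days; 1.4/56 = 2.5% of recurrences.

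**Overstatement of the RBX2660 success rate** (share missed × recurrence rate):

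| Case | Share missed | 20% recur | 30% recur | Subjects of 150 |
|---|---|---|---|---|
| Uniform visits, failure wording | 2.5% | 0.5 point | 0.75 point | 0.75–1.1 |
| Uniform visits, success wording | 3.3% | 0.7 point | 1.0 point | 1.0–1.5 |
| Every visit on day 49, success wording | 12.5% | 2.5 points | 3.75 points | 3.8–5.6 |

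Under uniform visits, 7 of 15 visit days (47%) fall before day 56.

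**Sensitivity to the timing of recurrence.** With a Weibull time to recurrence and F the recurrence by day 56, the share of subjects recurring on days 50–56 is (1−F)^((49/56)^k) − (1−F). This applies when every visit is on day 49.
- Constant hazard (k = 1): 0.8^0.875 − 0.8 = 2.3 points at F = 20%; 0.7^0.875 − 0.7 = 3.2 points at F = 30%.
- Early clustering (k = 0.5): 1.2 and 1.6 points.

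With uniform visits and constant hazard, the averages are 0.6 and 0.85 point.

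**The case against.** The strongest reply is that failure is not determined only at Visit 4. Protocol 3.7 and SAP 4.1.5 have the investigator determine failure when CDI recurs. Subjects are told to call if symptoms return (Protocol 6.5 and 6.6). A stool sample is requested if CDI recurs before 56 days (Protocol 6.4.1). All CDI episodes go on a dedicated eCRF (Protocol 3.7). Protocol 6.8 makes success depend on no recurrence before day 56, not on status on the visit day. After withdrawal, sites are asked to make every attempt to complete the later calls (Protocol 4.4).

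Much of this stands. A reader might infer that every recurrence on days 50–56 after an early visit is lost. The documents do not support that: for a subject who stays in the study, such a recurrence is likely to be recorded. What is missing from the visible text is a rule that it revises a success already scored. For a subject lost after an early Visit 4, nothing closes the gap.

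Redaction is a further caution. The remaining schedule footnotes in SAP 6.1, the text between SAP 6.1 and 6.3, and parts of SAP 4.1.4, 4.1.6 and 8.7.1 and Protocol 6.8 and 6.9 are blacked out. A rule for early visits could sit there. The visible wording of SAP 6.3 would still need correcting.

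A reader might also infer that the window favours RBX2660 over the controls. That is not shown. The controls' follow-up rule is not visible. SAP 6.3 draws the Evaluable Population from the Full Analysis Set, which includes the controls, so the same tolerance nominally covers them. Chart records without scheduled contacts may miss late recurrences too.

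**Conclusion.** The point holds as a defect in the definition of the primary analysis set and in the scoring rule. A success can be counted with up to 7 days of the endpoint window unobserved, or 6 under the failure wording. The likely overstatement of the RBX2660 rate is small, about 0.5–1.0 point or roughly 1 of 150 subjects, under the assumed 20–30% recurrence, even onset and uniform visit days. The 2.5–3.8 point figure is the upper bound at those rates; it needs every visit on day 49 and no later detection. Both shrink if recurrences cluster early or are reported afterwards.

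The direction is certain only within the RBX2660 arm. The documents do not support a claim that the primary comparison is biased in favour of RBX2660, or that successes have been wrongly counted. The correction is worth making because it bears on the primary endpoint and costs little.

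**What to change.** 1. In SAP 6.3, replace the day 49–63 range with a requirement that recurrence status is known through day 56.
2. State that the primary outcome is classified by the onset date of diarrhea, retreatment or fecal transplant, using all data, including the CDI episodes eCRF and the 3-month call. Let this override a score given at an early Visit 4.
3. Treat a subject last observed before day 56 without failure as not evaluable in the primary analysis and as missing in the Full Analysis Set analyses. Report how many there are, because the best-case imputation in SAP 8.7.1 would count them as successes again.
4. Apply the same rule to the historical controls and state it.
5. Reconcile the success wording (through day 56) with the failure wording (before day 56).

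Changing the Visit 4 window is optional. It would be a protocol amendment needing the approvals in Protocol 9.15, and the steps above do not depend on it.

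Cost: a few sentences in the SAP and no new visit, since the 3-month call already covers CDI symptoms (Protocol 3.2) and concomitant medications (Protocol 6.9). A few subjects may become non-evaluable, and the success rate may be slightly less favourable.
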